An initial pilot safety study will assess the risk of an infant overheating and/or experiencing lowered respiration via measurement of vital signs in a controlled clinical environment while wearing a weighted wearable blanket. Participants will also be observed for any hindrance in their ability to move due to the weighted wearable blanket. A member of the study team will be present during the intervention and continuously monitor the infant's vital signs, allowing for immediate evaluation and correction if needed. We plan to expand this study to include an at-home cohort in the near future (see secondary objective).

Objectives

- Primary Objective:**
 To pilot an investigation on the impact of weighted wearable blankets on vital signs and infant movement in healthy infants during nap polysomnogram.
- Secondary Objective:**
 To investigate the efficacy of weighted wearable blankets on sleep patterns in healthy infants during overnight sleep.

Outcome Measures/Endpoints

Endpoints	Measurement	Timeframe
Heart Rate	EKG	At start, duration of nap
Respiratory Rate	Respiratory effort belts	At start, duration of nap
Body Temperature	Manual recording (Ear thermometer)	At start (before wrapping the participant in the blanket); at the end of the study and during a (feed) break (before unwrapping the participant from the blanket)
Oxygen Saturation	Pulse oximetry	At start, duration of nap
Infant Movement	Observation	Duration of nap

Eligibility

The target population for this study are healthy infants, aged 0-12 months, weighing at least 8 or more lbs. Individuals of any sex, race or ethnicity may participate. The study population is restricted to this specific age group because the objective is focused on the safety and efficacy of weighted wearable blankets on infants.

Inclusion Criteria

- Ability of parent, caregiver or legal guardian/representative to understand a written informed consent document and choose to participate in the study.
- 0-12 months of age
- Weight \geq 8 lbs
- Gestational age \geq 37 weeks
- Health status: healthy infant without underlying cardiac, neurological, or pulmonary disorders.
- Infant is naive to a weighted wearable blanket.

Exclusion Criteria

1. Health status: medical diagnosis associated with underlying cardiac, neurological, or pulmonary disorder.
2. Weight < 8 lbs
3. Gestational age < 37 weeks
4. Gestational use of marijuana, alcohol, or illicit drugs
5. Home environment: use of cigarettes, vaping, e-cigarettes, or marijuana
6. Infant is not naive to a weighted wearable blanket.

Study Design

Direct observational pilot study of the safety of weighted wearable blankets on a minimum of (10) healthy infants aged 0-12 months with nap polysomnogram. Participants will be placed in a weighted wearable blanket, in accordance with their age/weight/height, by their parent or caregiver under the supervision of a member of the study team. After being put to sleep on their back, the participant will remain in the weighted wearable blanket until completion of the nap polysomnogram.

Enrollment/Recruitment

The target number of total participants is a minimum of 10 infants. The recruitment strategy aims to achieve representation of minority groups that reflects the demographics of the population in the catchment area. At least 5 infants must be 0-3 months and all others can be any age between 0 and 12 months of age.

Participants will be recruited in a variety of ways:

Flyers will be posted in the hospital(s) and/or on campus in places frequented by potential participants (e.g., elevators, food courts, parking garage elevators) or public places such as parks, grocery stores or churches. In addition, we will provide flyers and/or brochures to the various maternity wards at Riley, University & Methodist.

Brochures will be available for patients referred to the Sleep Center at Riley or established patients at a clinic visit. Patients who are already scheduled for a sleep study, and meet eligibility criteria, will be contacted by phone and introduced to the study. If the patient is interested, we will send the brochure and the consent (either by USPS or email).

The flyers and brochures will be shared with faculty physicians (in the division of Pediatric Pulmonology, Allergy and Sleep Medicine) as well as RN and other staff in the Sleep Center and maternity wards (for informational purposes only, they will not consent subjects). We might also include the flyer in weekly newsletters and/or internal communications.

Social media ads will be placed on Facebook and/or Instagram and clicking on this ad will direct potential participants to the study's web site

(<https://dreamlandbabyco.com/pages/clinical-trial>) where they can find phone and email information for the study team.

Study Procedures

During this study, participants will have one study visit. This visit will take place in the Sleep Center at Riley Hospital for Children at IU Health.

- Informed consent – we will explain the study and ask for written consent; participants will receive a signed copy of the consent to keep
 - depending on how the participant was recruited, the informed consent discussion and written consent may have already occurred virtually
- Review of inclusion/exclusion criteria
- Collection of demographic data (infant age, sex, weight) and review of clinical data (current medications, other non-pharmacologic interventions, evidence of cardiac, neurological, or pulmonary disorders) from participant medical records and parent report
- Vital signs measurements (heart rate, respiratory rate, body temperature, oxygen saturation) will be obtained at baseline and monitored throughout the sleep study
- Height and weight measurements will be obtained once, at baseline
- Participants will be placed in weighted wearable blanket such that the blanket does not cover the head/face or restrain the infant
- Participants will then be put to sleep on their backs
- Vital signs will be monitored over a 6–8-hour period with standard polysomnography equipment
- Upon infant awakening at the end of the nap, the weighted wearable blanket will be removed, and vital sign measurements will be repeated
- One week after the nap polysomnogram, subjects will be contacted by phone to complete a short questionnaire

The following stopping parameters will be used for this study. Parameters are noted when the infant is quietly sleeping and the changes observed are not due to agitation or crying. Baseline data will be recorded before and after placing the infant into the weighted, wearable blanket.

Endpoint	Stopping Parameters
Heart rate	Persistent increase by >20 from baseline for 15 minutes
Respiratory rate	Persistent increase by >10 from baseline for 15 minutes
Body temperature	Increase by more than 2° from baseline
Oxygen saturation	Persistent drop by >10% from baseline
Infant movement	Agitation and unable to settle to sleep >15 minutes

If any of the stopping parameters are met, the weighted blanket will be opened to assess if the weighted blanket is responsible for the change. If determined yes, the weighted blanket will be removed and the nap polysomnogram will be terminated.

Reportable Events

We will follow the IU HRPP Reportable Events Policy and Guidance, as needed. Severe adverse events (SAEs) will be reported to the FDA in accordance with 21 CFR 312.32.

An adverse event (AE) is defined as any untoward medical occurrence associated with the use of a drug or device in humans, whether or not considered drug- or device-related. An SAE is defined as an adverse event or suspected adverse reaction is considered "serious" if, in the view of the investigator, it results in any of the following outcomes: Death, a life-threatening adverse event, inpatient hospitalization or prolongation of existing hospitalization, a persistent or significant incapacity or substantial disruption of the ability to conduct normal life functions, or a congenital anomaly/birth defect. Important medical events that may not result in death, be life-threatening, or require hospitalization may be considered serious when, based upon appropriate medical judgment, they may jeopardize the patient or participant and may require medical or surgical intervention to prevent one of the outcomes listed in this definition. Collection of AEs and SAEs will begin at the time of consent.

Loss of confidentiality is always a potential adverse event and will be reported per existing Indiana University and Indiana University Health policies.

Study Withdrawal/Discontinuation

Participants are free to withdraw from participation in the study at any time for any reason.

The study team may discontinue a participant from the study for any of the following reasons:

- Unacceptable adverse event(s)
- Significant study intervention non-compliance
- The participant meets an exclusion criterion (either newly developed or not previously recognized) that precludes further study participation

Statistical Considerations

Sample Size Considerations

In the pilot safety study, the total sample size will be a minimum of 10 infants. All participants will receive the same intervention. Data from all participants who complete both baseline and follow-up assessments will be included in the analysis.

Statistical Analysis Plans:

Primary Analysis (Safety)

Means and standard deviations for each vital sign will be calculated at both baseline and during the intervention. Summary statistics based on demographic and baseline characteristics will be gathered. A Paired t-test will be performed to compare the means

of each vital sign at baseline and during the intervention. We will also use a linear mixed effect model to determine differences in vital signs.

The t-statistic and corresponding p-value will be calculated at a significance level of 0.05 alpha. If the p-value is less than 0.05, this will be interpreted as a statistically significant difference in the vital sign before and after wearing the weighted wearable blanket. If the p-value is greater than 0.05, this will be interpreted as no significant difference in the vital sign before and after wearing the weighted wearable blanket.

Reporting and Documentation of Results

Measures and Instruments

Polysomnography (PSG) Equipment

PSG will be conducted using a multi-channel PSG system Respiration Alice G3 that is designed for sleep studies. The system will include the following components: Electroencephalography (EEG) to measure brain activity, Electromyography (EMG) to monitor muscle activity, Electrooculography (EOG) to record eye movements, Electrocardiography (ECG) for heart rate monitoring, Respiratory effort belts to measure chest and abdominal movements, Nasal and oral airflow sensors to monitor airflow, Pulse oximetry to measure oxygen saturation levels, and Video recording for behavioral monitoring during sleep. Prior to each PSG recording, the equipment will be calibrated according to American Academy of Sleep Medicine (AASM) guidelines to ensure accurate measurements, and quality control checks will be performed regularly to ensure proper functioning of sensors and electrodes during the study. The following physiological variables will be continuously measured and recorded during PSG:

- Electroencephalography (EEG): EEG electrodes will be placed according to the international 10-20 system to record brain activity and identify sleep stages (e.g., wake, NREM, REM).
- Electromyography (EMG): EMG electrodes will be positioned to monitor muscle activity, including chin and limb muscles, to assess muscle tone and movements during sleep.
- Electrooculography (EOG): EOG electrodes will be used to detect eye movements, which are important for distinguishing sleep stages and identifying rapid eye movement (REM) sleep.
- Electrocardiography (ECG): ECG electrodes will be placed to monitor heart rate and detect any cardiac abnormalities during sleep.
- Respiratory Parameters: Respiratory effort belts will record chest and abdominal movements to assess breathing patterns; Nasal and oral airflow sensors will measure airflow and detect apnea and hypopnea events; and Pulse oximetry will monitor oxygen saturation levels.

Privacy/Confidentiality

All study data will be treated as confidential information. Similarly, the participant's medical history will also be treated as confidential with no identifiable information released or shared with individuals outside the study team.

Follow-up and Record Retention

All study records will be kept in a secured office or locked file cabinet or on a password protected computer server at the study site. Only the study investigators and research team will have access to the link between the participant information. Information linking a participant's name to a participant identification number will be stored securely.

Regulatory Compliance

This study will be carried out in accordance with International Conference on Harmonisation Good Clinical Practice (ICH GCP). Study investigators and clinical trial site staff who are responsible for the conduct, management, or oversight of clinical trials have completed Human Subjects Protection and ICH GCP Training.

The protocol, the proposed informed consent form, recruitment materials, and all subject-facing materials will be submitted to the Institutional Review Board (IRB) for review and approval. Approval of both the protocol and the consent form must be obtained before any participants are enrolled. Any amendment to the protocol will require review and approval by the IRB before the changes are implemented to the study. In addition, all changes to the consent form will be IRB-approved; a determination will be made regarding whether a new consent needs to be obtained from participants who provided consent, using a previously approved consent form.

References

3. Ponsonby A-L, Dwyer T, Gibbons LE, Cochrane JA, Jones ME, McCall MJ. Thermal environment and sudden infant death syndrome: case-control study. *BMJ* 1992;304:277-82
4. Ponsonby A-L, Dwyer T, Gibbons LE, Cochrane JA, Wang Y-G. Factors potentiating the risk of sudden infant death syndrome associated with the prone position. *N Engl J Med* 1993;329:377-82

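### No replicate ear readings are planned for body temperature, the only direct measure of overheating; if one reading is taken each time, its error enters the paired difference and is at best partly diluted

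*Combined protocol and SAP*

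**What the plan says.** The overview before the Objectives states the aim: "An initial pilot safety study will assess the risk of an infant overheating and/or experiencing lowered respiration". In the Outcome Measures/Endpoints table, temperature is a "Manual recording (Ear thermometer" reading. Its baseline is "At start (before wrapping the participant in the blanket", and its later readings are taken "at the end of the study and during a (feed) break (before unwrapping the participant from the blanket". The other three vital signs are recorded for the whole nap, and the polysomnography channels listed under Measures and Instruments include no temperature sensor.

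Study Procedures describes the timing differently. It says "Baseline data will be recorded before and after placing the infant into the weighted, wearable blanket", and that when the infant wakes at the end "the weighted wearable blanket will be removed, and vital sign measurements will be repeated".

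Primary Analysis (Safety) says "Means and standard deviations for each vital sign will be calculated at both baseline and during the intervention". It then plans a paired t-test of baseline against intervention for each vital sign, and a linear mixed effect model. Sample Size Considerations sets a minimum of 10 infants.

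Nowhere does the document state how many ear readings make up a time point, which ear is used, or how the feed-break and end readings are combined. It gives no SD, thermometer error or target precision.

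**The concern.** A continuously recorded signal averages out much of its moment-to-moment device noise. A hand-held ear reading taken at isolated moments does not. If each time point is one reading, the reading error of both ends goes into the infant's change. Switching ears, or using an ear that has been lain on, could add a further difference unrelated to core temperature (assumption).

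With about 10 paired differences, this noise widens the interval for the mean temperature change. The plan reads a p-value above 0.05 as no significant difference. In a safety study, avoidable noise pushes towards that reading on one of the two hazards the pilot was set up to examine. The remedy uses a thermometer already in hand, at moments when temperature is being taken anyway.

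**Working it through.** The plan states no precision or power figure for temperature, so there is none to reproduce. The check asks how much replicate readings would narrow the interval.

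**Inputs**
- From the document: n = 10 (the minimum), paired comparison, alpha 0.05. Sidedness is not stated; two-sided is assumed.
- Assumed: SD of the true change between infants b = 0.3 °C; error SD of one reading m = 0.2 or 0.3 °C.

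**Formula**
Half-width = t(0.975, 9)/√10 × SD of the difference = 0.715 × SD of the difference. The variance of the difference is b² plus the error variance of the baseline value plus that of the on-blanket value.

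| Readings | Variance | m = 0.2 | m = 0.3 |
|---|---|---|---|
| One per side | b² + 2m² | 0.170 → 0.295 °C | 0.270 → 0.372 °C |
| Three per side, independent errors | b² + 2m²/3 | 0.117 → 0.244 °C | 0.150 → 0.277 °C |
| Three per side, half the error variance shared within a session | b² + 4m²/3 | 0.143 → 0.271 °C | 0.210 → 0.328 °C |
| One at baseline, feed-break and end readings averaged | b² + 1.5m² | 0.150 → 0.277 °C | 0.225 → 0.339 °C |

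In the third row, each side keeps m²/2 in full and one third of the other m²/2. That is 2m²/3 per side, or 4m²/3 in all.

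**Reduction against one reading per side**
- Three readings, independent errors: 1 − √(0.1167/0.17) = 0.172 and 1 − √(0.15/0.27) = 0.2546, so about 17% and 25%.
- Three readings, half the error shared: 1 − √(0.1433/0.17) = 0.082 and 1 − √(0.21/0.27) = 0.118, so about 8% and 12%.
- No replicates, two on-blanket readings averaged: 1 − √(0.15/0.17) = 0.061 and 1 − √(0.225/0.27) = 0.087, so about 6% and 9%. This assumes the same true change at both on-blanket times.

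**What replicates add after on-blanket averaging**
With three independent readings at baseline, feed break and end, the variance is b² + m²/3 + m²/6 = b² + m²/2, which is 0.110 and 0.135. Against the last row of the table, the further reduction is 1 − √(0.110/0.150) = 0.144 and 1 − √(0.135/0.225) = 0.225, so about 14% and 23%.

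**Wider range of assumptions**
For b from 0.1 to 0.4 °C and m from 0.1 to 0.3 °C, with one reading per side as the comparator, three readings narrow the interval by 4% to 39% with independent errors. With half the error variance shared, the range is 2% to 17%.

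**The case against.** **The number of readings is not stated.** A reader might infer that the protocol prescribes exactly one reading. It does not: it gives an instrument and time points. One reading is the natural interpretation of silence, so the point is conditional on it. The silence also leaves operators free to differ.

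**The error may already be diluted.** A reader might also infer that thermometer error passes into the comparison in full. That holds only for one baseline reading against one on-blanket reading. A feed-break reading, a possible second baseline or the mixed model could each reduce it. This objection stands in part. The plan does not define the contrast or say that every infant will have a feed break, and averaging the on-blanket readings leaves the baseline error untouched.

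**Consecutive readings share error.** Placement, ear canal and device effects within a session may be common to all three readings, and averaging removes only the independent part. This stands, and is why the smaller gain is reported beside the larger.

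**No decision is shown to change.** At the assumed SDs with one reading per side, the half-width falls by 0.05 to 0.09 °C with independent errors (0.295 − 0.244; 0.372 − 0.277). The only temperature change the protocol specifies is a stopping parameter of more than 2°, scale not stated. That parameter applies to an individual infant, not to the mean change, but the gain is still modest.

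**Temperature is not shown to be the weakest endpoint.** A reader might infer that, of the four vital signs, it is the most likely to end inconclusively. The document gives no SD or expected effect for any of them, and continuous recording does not remove variation between infants, so that ranking is unsupported.

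**The lain-on ear may seldom matter.** Infants are put down on their backs, which weakens the mechanism. Insisting on both the same ear and an ear not lain on could also be impossible for a given infant.

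**Conclusion.** The point holds as a low-cost refinement. Temperature is the only one of the four vital signs taken by hand at isolated moments, it is the only direct thermal measure, and no replicates are planned. Unless reading errors are fully shared within a session, averaging replicates narrows the expected interval.

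The direction is secure; the size is not. The reduction of about 17% to 25% rests on a true-change SD of 0.3 °C, a reading-error SD of 0.2 to 0.3 °C, 10 infants, one reading per side and independent errors. Sharing half the error variance cuts it to about 8% to 12%. None of these SDs comes from the document.

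Replicates do not settle a separate conflict. The endpoints table takes the end temperature before unwrapping, whereas Study Procedures repeats vital signs after the blanket is removed. The endpoints table has a baseline before wrapping only, whereas Study Procedures records baseline data before and after placement. Until these are reconciled, it is unclear what the temperature difference measures.

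**What to change.** - In the Body Temperature row, specify three consecutive readings at each scheduled time point, in the same ear throughout where possible. Record which ear was used and whether it had been lain on.
- Analyse the mean of the three. Keep the single readings, so that the pilot also yields a within-session reading-error SD for planning the at-home cohort.
- In Primary Analysis (Safety), state how the feed-break and end temperatures form the on-blanket value, and what is done when there is no feed break.
- Reconcile the endpoints table with Study Procedures on whether the end temperature is taken before or after blanket removal, and on which baseline reading enters the paired difference.

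The cost is about one extra minute of handling per time point (assumption; the document gives no burden data), with the thermometer already in use and no added visit. The other changes are edits to the text.

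### Infants awaiting a clinical sleep study may be enrolled as healthy, because neither health criterion addresses a suspected disorder still under investigation

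*Combined protocol and SAP*

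**What the plan says.** All references are to the combined protocol and SAP.

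- **Population.** Eligibility states: "The target population for this study are healthy infants, aged 0-12 months, weighing at least 8 or more lbs". The primary objective concerns the effect "on vital signs and infant movement in healthy infants during nap polysomnogram".
- **Recruitment.** Enrollment/Recruitment includes two sleep-clinic routes: "Brochures will be available for patients referred to the Sleep Center at Riley or established patients at a clinic visit", and "Patients who are already scheduled for a sleep study, and meet eligibility criteria, will be contacted by phone and introduced to the study". The other routes are flyers, maternity wards, newsletters or internal communications, and social media.
- **Health criteria.** Inclusion: "Health status: healthy infant without underlying cardiac, neurological, or pulmonary disorders". Exclusion: "Health status: medical diagnosis associated with underlying cardiac, neurological, or pulmonary disorder".
- **Screening.** Study Procedures calls for a check of both lists of criteria and a review of clinical data, including "evidence of cardiac, neurological, or pulmonary disorders) from participant medical records and parent report". The reason for a sleep referral and the recruitment route are not among the data listed.
- **After entry.** Study Withdrawal/Discontinuation lets the team discontinue an infant in this case: "The participant meets an exclusion criterion (either newly developed or not previously recognized) that precludes further study participation".
- **Analysis.** Sample Size Considerations sets a minimum of 10 infants in one group and analyses everyone with baseline and follow-up data. The primary analysis compares baseline with intervention means by a paired t-test, with a mixed model in addition. Neither separates infants by recruitment source.

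**The concern.** An infant with a scheduled clinical sleep study may be under investigation for a problem that has not yet been confirmed or ruled out. The plan approaches these infants for a study whose conclusion is about healthy ones, and leaves their status to whoever applies the word healthy, which the protocol does not define.

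Two things are at stake. The first is the population: if some participants have an unrecognised disorder, the pooled means no longer describe the group named in the primary objective. The second is interpretation. Saturation, respiratory rate and heart rate during sleep are the study's endpoints, and they are also what a sleep referral may concern. There is a participant-protection side too, since infants under investigation would be exposed under a protocol whose stated population is healthy.

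**Working it through.** The plan gives no figure on this point, and the minimum of 10 comes without an effect size, standard deviation or power. There is nothing to reproduce, so the check is mainly a reading of the text.

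**1. Can an infant under investigation be judged eligible?**

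| Infant's status | Inclusion (no underlying disorder) | Exclusion (diagnosis) | Outcome |
|---|---|---|---|
| Disorder diagnosed | fails | excluded | not eligible |
| Disorder present and recognised from the records, no formal diagnosis | fails | not triggered | not eligible |
| Disorder suspected, sleep study pending | depends on the meaning of healthy | not triggered | not determined by the text |
| No disorder suspected | passes | not triggered | eligible |

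The third row is the gap. The condition in the recruitment sentence that criteria be met only refers back to these two lines. The records and parent report may hold nothing confirmed for an infant whose investigation has not been done. No step requires the referral reason to be checked, or the clinical study to be read as normal first.

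**2. Does pairing within infants remove the problem?**

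Write each infant's difference (during minus baseline) as D = b + s + u, where b is the blanket effect, s the ordinary change from baseline to sleep, and u any extra change in sleep due to an unrecognised disorder. A stable difference between infants cancels in D; u does not.

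To separate u from b, the infant would have to be measured asleep without the blanket. Study Procedures lists baseline vital signs, then placement in the blanket, then putting the infant to sleep. Stopping-rule baseline data are recorded before and after placement in the blanket. Study Design keeps the infant in the blanket until the polysomnogram ends, and the repeat measurements after removal follow awakening. No unblanketed sleep period and no control group are described, so u enters D as if it were part of b.

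**3. How large could it be?**

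With k such infants among n, and an average extra change u, the shift in the mean difference is (k/n) × u.

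- At n = 10: k = 1 gives 0.1u, k = 3 gives 0.3u, k = 5 gives 0.5u.
- Ten is a minimum. With more infants, each one's weight is 1/n and so smaller.
- The documents give neither k nor u.

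For the chance that the problem arises at all, let q be the assumed probability that an enrolled infant has an unrecognised disorder. Then P(at least one of 10) = 1 − (1 − q)^10:

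| q (assumed) | P(at least one of 10) |
|---|---|
| 0.05 | 1 − 0.95^10 = 40% |
| 0.10 | 1 − 0.90^10 = 65% |
| 0.20 | 1 − 0.80^10 = 89% |
| 0.30 | 1 − 0.70^10 = 97% |

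No value of q is supported by the documents. The table shows only that a small q would not make the event rare in 10 infants.

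**4. How precise would a sensitivity analysis be?**

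A two-sided paired t-test at 0.05 has 80% power for a mean change of about 1.00 SD of the differences with 10 infants, and about 1.07 SD with 9. Removing referred infants can therefore be descriptive only.

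**The case against.** The strongest reply is that eligibility already covers this. The inclusion criterion does not depend on a diagnosis, the phone approach is limited to infants who meet the criteria, the record review looks for evidence of disorder (broader than a diagnosis), and an infant found later to meet an exclusion criterion can be discontinued.

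Much of that stands. A reader might infer that only an existing diagnosis keeps an infant out, or that every infant booked for a sleep study passes the criteria as written. The documents support neither: an infant known to have a disorder fails inclusion even without a formal diagnosis, and one with a suspected disorder is a judgement call. The reply does not settle that judgement call. Healthy is undefined, and the discontinuation provision is discretionary and tied to the exclusion list, where the health item is the diagnosis-worded one.

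Three further points are fair:

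- **Reason for booking.** The documents do not say why these infants are scheduled. Investigation of a breathing problem is a reasonable inference, not a stated fact.
- **Attribution.** A reader might infer that an event could not be attributed at all. In fact, when a stopping parameter is met, the blanket is opened to assess whether it is responsible. That step is imperfect, and it helps only with events that reach a stopping parameter, not with a shift in the means.
- **Design.** The ordinary change from baseline to sleep is mixed with the blanket effect in every infant, whatever the recruitment route. That limitation is separate. Referred infants may add a further component that the healthy-infant sample is meant to keep out.

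**Conclusion.** The concern holds as a gap in eligibility and data recording. The plan actively recruits from infants scheduled for clinical sleep studies, its two health criteria use different tests, and neither covers a suspected disorder under investigation. Such an infant may be enrolled and pooled with the rest, with no planned record of route or referral reason by which to identify the infant afterwards.

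The consequence for the paired comparison rests on the order of procedures as listed: baseline before sleep, and no sleep without the blanket. On that reading, a breathing problem that emerges in sleep is counted as a blanket effect.

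Each infant carries 10% of the mean at the minimum sample size. Beyond that the size is unknown, because the number of referred infants and their response would both have to be assumed. For a sleep-related breathing disorder, a shift towards lower saturation is plausible. The documents do not establish a direction for the other endpoints or disorders, and they do not show that any bias will occur.

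**What to change.** 1. **Align the health criteria.** Define healthy, and word inclusion and exclusion to the same standard.
2. **Add one exclusion line**, for example: *pending or unresolved investigation, including a scheduled clinical sleep study, for a suspected respiratory, cardiac or neurological problem.*
3. **Record two items for every infant:** recruitment route, and the reason for any sleep or clinic referral.
4. **Report by route.** List individual results by recruitment route, and show the primary summaries with and without any sleep-clinic referrals, labelled as a descriptive sensitivity check and not a test.

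The cost is an eligibility edit, two data fields, one listing and one table. Part of one recruitment source is lost, but flyers, maternity wards, newsletters and social media remain for a minimum of 10 infants. The sensitivity table will be imprecise at about that number, which is why the individual listing should accompany it.
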